#### **11.4.3.3 Analysis of vital signs data**

The summary statistics (including number, mean, median, SD, minimum and maximum) of all vital signs variables will be calculated for each visit or study assessment (baseline, each post-baseline time point, endpoint) by treatment group.

The incidence of PCSA at any time will be summarized by treatment group for each vital signs variable. Shift tables showing changes with respect to the baseline status will be provided. Listings will be provided with flags indicating the out of range values as well as the PCSA values.

#### **11.4.3.4 Analysis of immunogenicity data**

At each sample time, the result of the ADA assay will be categorized as either positive or negative. ADA positive samples will be further characterized as either neutralizing or non-neutralizing. Descriptive statistics will be provided for:

ADA positive patients are defined as:

- Treatment Emergent Responses: Patients with no positive assay response at baseline but with a positive assay response during the TEAE period or
- Treatment Boosted Responses: Patients with a positive ADA assay response at baseline and also have at least a 4-fold increase in titer over baseline titer during the TEAE period.

ADA negative patients are defined as any evaluable patient that is not an ADA positive patient.

Descriptive statistics for ADA titers will be provided for patients with positive ADA assay response and selected sub-categories.

Efficacy/safety endpoints will be analyzed for the subgroup of ADA positive patients during the TEAE period and compared to ADA negative patients.

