- b Last administration of sarilumab is at Week 50. Patients will be monitored for at least 30 minutes or up to 2 hours as per country specific requirements after each dose of SC IMP for any signs or symptoms of a hypersensitivity reaction.
- c Patient Reported Outcomes include EQ-5D-3L, FACIT-Fatigue, SF-36v2, HAQ-DI
- d Bone Mineral Density assessment will be performed at the baseline (Visit 2) and Week 52 (Visit 12) using a DXA scan. The scan can be performed within ± 14 days of Visit 2 and within -14 days of Visit 12 and needs to include the lumbosacral and femoral neck regions. However, the baseline visit DXA scan is not required if there is one available within 12 weeks of baseline.
- e Chest X-ray is required during the screening period if no chest imaging (X-ray, CT, MRI) is available within the previous 12 weeks of V1 that clearly documents the exclusion of TB or if it does not follow the local guidelines and requirements for active screening of TB. In countries for which a specific approval procedure for the x-ray is required by a different committee than the local EC/IRB, a chest MRI between V1 and V2 can be performed.
- f Hematology (blood should be drawn before drug administration): Hemoglobin, hematocrit, red blood cell (RBC) count and morphology (if RBC count is abnormal), white blood cell (WBC) differential, platelet count, absolute neutrophil count (ANC).
- g Chemistry (blood should be drawn before drug administration): Sodium, potassium, chloride, bicarbonate, blood urea nitrogen (BUN), creatinine and creatinine clearance, calcium, phosphate, total protein, albumin, alanine aminotransferase (ALT) (SGPT), aspartate aminotransferase (AST) (SGOT), alkaline phosphatase (ALP), total bilirubin, conjugated bilirubin, unconjugated bilirubin, lactate dehydrogenase (LDH), uric acid
- h Anti-nuclear antibody (ANA) will be collected at Visit 2 and EOT visits only.
- i Lipids (blood should be drawn before drug administration): Triglycerides (TG), total cholesterol, high density lipoprotein (HDL) cholesterol, low density lipoprotein (LDL) cholesterol. Fasting is defined as having no food or liquid intake (except water/ice) for six hours or more.
- j Blood should be drawn before drug administration. Fasting is defined as having no food or liquid intake (except water/ice) for six hours or more.

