#### **11.4.3 Analyses of safety data**

The summary of safety results will be presented by treatment group. Incidence rates and exposure adjusted event summaries will be provided for categorical safety summaries.

All safety analyses will be performed on the safety population using the following common rules:

- The baseline value is defined generally as the last available value before randomization.
- The observation period to be used for the safety population is the TEAE period. The TEAE period is defined as the time from first dose of randomized study treatment to the last dose date of IMP +60 days.
- For quantitative safety parameters based on central laboratory/reading measurements, descriptive statistics will be used to summarize results and change from baseline values by visit and treatment group.
- The analysis of the safety variables will be essentially descriptive and no hypothesis testing is planned.

The following definitions will be applied to laboratory parameters, vital signs and ECG.

- The potentially clinically significant abnormality (PCSA) values are defined as abnormal values considered medically important by the Sponsor according to predefined criteria/thresholds based on literature review and defined by the Sponsor for clinical laboratory tests, vital signs, and ECG.
- PCSA criteria will determine which patients had at least 1 PCSA during the on-treatment period, taking into account all evaluations performed during the on-treatment period, including unscheduled or repeated evaluations. The number of all such patients will be the numerator for the on-treatment PCSA percentage.

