2.1.5 Immunogenicity endpoints

The immunogenicity blood samples will be collected before injection during the same visit according to the Study Flow Chart ([Appendix A](#)).

Samples analyzed in the antidrug antibody (ADA) assay will be categorized as either positive or negative, and in the case of a positive result will be further characterized as either neutralizing or non-neutralizing.

ADA positive patient is defined as patient with at least one treatment-emergent or treatment-boosted ADA positive sample during the TEAE period, where

- Treatment-emergent ADA positive patient is defined as a patient with non-positive assay (meaning negative or missing) response at baseline but with a positive assay response during the TEAE period.

- Treatment-boosted ADA positive patient is defined as a patient with a positive ADA assay response at baseline and with at least a 4-fold increase in titer compared to baseline during the TEAE period.

ADA negative patient is defined as patient without a treatment-emergent or treatment-boosted ADA positive sample during the TEAE period.

A treatment-emergent positive response is further classified as persistent or transient.

Persistent ADA response: treatment-emergent ADA detected at two or more consecutive sampling time points during the TEAE period, where the first and last ADA positive samples are separated by a period of at least 16 weeks. Also persistent in case last sample analyzed is positive.

Transient ADA response: A treatment-emergent response that is not determined to be persistent.

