2.3.3 Pharmacokinetics and ADA populations

The PK population will consist of all patients in the safety population with at least one post-dose, non-missing serum sarilumab concentration value. The ADA population will consist of all patients in the safety population with at least one post-dose, evaluable ADA sample. Patients will be analyzed according to the treatment actually received.

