The safety assessment will focus on the following events:

- Hypersensitivity (standardized MedDRA query (SMQ): Hypersensitivity [Narrow]).
- Anaphylaxis (SMQ: Anaphylaxis [Narrow]).
- Injection-site reactions (HLT: Injection site reactions).
- TEAEs leading to permanent treatment discontinuations.

Number (%) of patients with these events will be summarized by ADA patient classifications (positive or negative) for the sarilumab treatment group. The relationship between the timing and the titer of the positive ADA and events may also be explored as necessary.

ADA and clinical efficacy

The following efficacy endpoints will be analyzed by ADA patient classifications (positive or negative; persistent, transient; neutralizing, non-neutralizing):

- Proportion of patients achieving sustained remission at Week 52
- Number (%) of patients with lack of efficacy.

Lack of efficacy is defined as permanent treatment discontinuation due to lack of efficacy.

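### Week 52 efficacy is compared by an ADA status that runs past the outcome and depends on staying on injections, so the comparison can dilute or mask an adverse ADA association

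*Protocol*

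**What the plan says.** **Planned comparison.** Protocol 11.4.3.4: "Efficacy/safety endpoints will be analyzed for the subgroup of ADA positive patients during the TEAE period and compared to ADA negative patients".

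**Classification.** SAP 2.1.5: "ADA positive patient is defined as patient with at least one treatment-emergent or treatment-boosted ADA positive sample during the TEAE period". Its complement: "ADA negative patient is defined as patient without a treatment-emergent or treatment-boosted ADA positive sample during the TEAE period". Protocol 11.4.3 sets the period: "The TEAE period is defined as the time from first dose of randomized study treatment to the last dose date of IMP +60 days". SAP 2.1.4 gives the same limit, counted from the last SC dose.

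**Sampling.** The flow chart schedules ADA at baseline and Weeks 12, 24, 52 and 58. It also notes: "Last administration of sarilumab is at Week 50". SAP Appendix I keeps the Week 58 sample as the follow-up measurement. One sample is enough to be counted (SAP 2.3.3): "The ADA population will consist of all patients in the safety population with at least one post-dose, evaluable ADA sample".

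**Persistence.** After the 16-week rule, SAP 2.1.5 adds: "Also persistent in case last sample analyzed is positive".

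**Use.** SAP 2.4.8: "The following efficacy endpoints will be analyzed by ADA patient classifications (positive or negative; persistent, transient; neutralizing, non-neutralizing". The endpoints are sustained remission at Week 52 and lack of efficacy, and the latter is defined as permanent treatment discontinuation for that reason. Under SAP 2.1.3.1, permanent withdrawal from study treatment before Week 52 fails the composite.

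**Safety.** SAP 2.4.8 tabulates selected events by overall ADA class. Looking at their timing relative to the antibody is optional.

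Neither document describes a landmark, a time-varying analysis or any allowance for the number of samples.

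**The concern.** A comparison of efficacy by ADA status is read as evidence on whether antibodies cost efficacy. For that, status should be fixed before the outcome and should not depend on it. Neither holds here.

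- A first positive at Week 58 comes after the last injection and after the Week 52 outcome, yet it makes the patient ADA positive. As the last sample, it also makes the response persistent.
- Stopping injections does two things at once: it makes the patient a non-responder and it closes the ADA window 60 days later. Non-response by this route goes with fewer chances to test positive. The link is tightest for lack of efficacy, where the event is itself the stop.

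This is an immortal-time structure. At stake is a table that could reassure more than it should, not the primary comparison.

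**Working it through.** **1. Does the window include Week 58?** A dose at week k falls on Day 7k + 1, so Week 50 is Day 351 and the window closes on Day 351 + 60 = 411. Week 58 is Day 407, a gap of 56 days. With ±3 days on both dose and visit, the gap exceeds 60 in only 3 of 49 combinations (maximum 62). Week 58 is therefore normally inside.

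**2. Scheduled post-baseline samples inside the window** (7k + 1 + 60 set against Days 85, 169, 365 and 407):

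| Last dose at week | Window closes on Day | Samples |
|---|---|---|
| 0-2 | 61-75 | 0 |
| 4-14 | 89-159 | 1 |
| 16-42 | 173-355 | 2 |
| 44-48 | 369-397 | 3 |
| 50 | 411 | 4 |

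A patient who stops early should also have one sample at the premature EOT visit (Protocol 10.4.4), taken here to include ADA because the EOT procedures in Protocol 10.2.2.4 do.

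**3. How much rests on late samples?** Assume a constant conversion rate with a proportion I positive by Day 407. The share of positive completers first positive at Week 58 is 1 − [1 − (1 − I)^(365/407)]/I, which is 9.8% at I = 10% and 9.3% at I = 20%. Replacing 365 with 169 gives the share first positive at Week 52 or 58: 57% and 56%. Most of those are Week 52 samples, which pick up conversion between Weeks 24 and 52, inside the outcome period.

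**4. Apparent difference when antibodies have no effect.** The documents give no rates. Assume 45% remission in completers, 0% in discontinuers, a proportion d discontinuing, and a proportion I_d of discontinuers with a positive sample. Then

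- remission in positives = 0.45(1 − d)I / [(1 − d)I + d·I_d]
- remission in negatives = 0.45(1 − d)(1 − I) / [(1 − d)(1 − I) + d(1 − I_d)]

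A simulation with I = 20%, step 2's windows and the EOT sample gave 19.0% positive overall at d = 10% and 16.9% at d = 30%. Solving, I_d = (0.190 − 0.9 × 0.2)/0.1 = 10% and (0.169 − 0.7 × 0.2)/0.3 = 9.7%, so discontinuers have about half the completers' chance. With I_d = I/2:

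| d | I = 10%: positive v negative | Difference | I = 20%: positive v negative | Difference |
|---|---|---|---|---|
| 10% | 42.6 v 40.3 | +2.4 | 42.6 v 40.0 | +2.6 |
| 20% | 40.0 v 35.6 | +4.4 | 40.0 v 35.1 | +4.9 |
| 30% | 37.1 v 31.0 | +6.1 | 37.1 v 30.4 | +6.7 |
| 40% | 33.8 v 26.4 | +7.3 | 33.8 v 25.7 | +8.0 |

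Simulation at d = 40% reached 8.6. A Week 24 landmark (status by Week 24 among those still on injections) gives about zero. Cutting the window at Week 52 leaves +2 to +6 at 10-30% discontinuation.

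**5. When antibodies halve remission.** Simulated differences, in points:

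| Discontinuation | True | Planned rule | Cut at Week 52 | Week 24 landmark |
|---|---|---|---|---|
| 10% | −20 | −17 | −19 | −19 to −20 |
| 30% | −16 | −10 to −11 | −12 to −13 | −17 to −18 |

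**6. Can it go the other way?** Protocol 9.5.1 asks for ADA samples at the onset and completion of an SAE. If every discontinuer had both and antibodies lasted only 14 days, the no-effect difference became −0.5 (10% discontinuing) and −1.5 (30%).

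**7. Precision.** In 59 sarilumab patients, ADA rates of 5, 10 and 20% give about 3, 6 and 12 positives. The 95% half-width is 1.96·√[0.4 × 0.6 × (1/n₁ + 1/n₀)]: ±57 points (3 v 56), ±41 (6 v 53) and ±31 (12 v 47).

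**The case against.** The strongest case against is that this table cannot carry an inference anyway. SAP Appendix D lists immunogenicity as descriptive, SAP 2.4.4.4 tests only the primary endpoint and then cumulative CS dose, and half-widths of 31 to 57 points dwarf a bias of 2 to 8. All of that is true and limits the importance of the point. It does not remove a systematic lean in a table that may be quoted as showing no antibody effect.

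Three further objections stand in part.

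- A reader might infer that non-responders in general are pushed into the ADA-negative group. The documents do not support that: under Protocol 8.2, patients who flare and take rescue corticosteroids should continue injections, so they keep full sampling. Only those who stop injections are affected.
- A reader might see Week 58 as the main cause. It supplies the first positive in only about 10% of positive completers, and removing it leaves most of the bias. The larger part is unequal sampling.
- A landmark is not neutral. It drops anyone whose antibodies led to stopping before Week 24, counts later converters as negative, and in step 5 slightly overshoots the true difference at 30% discontinuation. It belongs beside the existing table, not in its place.

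**Conclusion.** The timing flaw follows from the documents: ADA status for the Week 52 comparison uses samples taken after the outcome, and stopping injections both fixes non-response and shortens the time in which antibodies can be found. The comparison can dilute or mask an adverse ADA association, by about 2 to 8 points in favour of ADA positives under 10-20% ADA and 10-40% discontinuation. Every such figure rests on assumed rates.

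It is tempting to conclude that the plan hides a harmful antibody effect, or that the bias can run only one way. The documents support neither: they give no ADA rate, discontinuation rate or antibody effect; real harm is usually shrunk, not removed (−20 shown as −17, −16 as −10 to −11); and SAE-triggered sampling can reverse the sign slightly. The primary analysis is untouched. This is a modest point, worth acting on because the remedy is cheap.

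**What to change.** In SAP 2.4.8:

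1. For the efficacy comparison, leave ADA samples taken after Week 52 out of the classification, including the persistent/transient label. Keep the TEAE-period definition for ADA incidence.
2. Beside the existing descriptive table, add a supplementary landmark display: ADA status by Week 24 among sarilumab patients still on injections at Week 24.
3. Report the number of evaluable ADA samples per patient by ADA class, so that unequal sampling is visible.
4. For the listed safety events, show whether each came before or after the first positive sample. Do not reclassify events: with 12 to 28 weeks between scheduled on-treatment samples, counting only events after the first positive would credit events from undetected antibodies to ADA-negative patients.

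**Cost.** SAP wording and derived flags from data already collected. The landmark groups will be very small: 59 × [1 − (1 − I)^(169/407)] gives 2.5 positives at I = 10% and 5.2 at I = 20%, before removing those who stopped. They omit patients who stopped before Week 24 and count later converters as negative. Item 1 is a partial cure only. With Week 58 removed, a first positive at Week 52 also becomes persistent under the last-sample rule, and a footnote should say so.

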#### **11.4.4 Analyses of pharmacokinetic and pharmacodynamic variables**

Serum concentrations of functional sarilumab will be summarized using arithmetic and geometric means, SD, standard error of the mean (SEM), coefficient of variation (CV%), minimum, median, and maximum by visit.

IL-6 and sIL-6R will be summarized using arithmetic and geometric means, SD, standard error of the mean (SEM), coefficient of variation (CV%), minimum, median, and maximum by visit.

#### **11.4.5 Analyses of patient reported outcomes**

Change from baseline in patient reported endpoints at Weeks 12, 24 and 52 will be analyzed with a mixed model repeated measures approach (all data is continuous):

- SF-36v2 physical component summary score.
- SF-36v2 mental component summary score.
- Each SF-36v2 domain (n=8).
- EQ-5D-3L single index utility score.
- EQ-5D-3L VAS score.
- FACIT-Fatigue total score.
- HAQ-DI standardized score.
- HAQ-DI pain score.
- HAQ-DI patient global assessment.

The model, including treatment, visit, treatment-by-visit interaction, as fixed effects and baseline score as a covariate, will be used to test the difference of least-square means (LS means) between treatment groups in each variable. Descriptive statistics including number of subjects, mean, standard error and LS means will be provided. In addition, difference in LS means, the corresponding 95% CI and the p-value will be provided.

#### **11.5 INTERIM ANALYSIS**

No interim analysis is planned for this study.

## **12 ETHICAL AND REGULATORY CONSIDERATIONS**

### **12.1 ETHICAL AND REGULATORY STANDARDS**

This clinical trial will be conducted by the Sponsor, the Investigator, and delegated Investigator staff and Sub-Investigator, in accordance with the principles laid down by the 18th World Medical Assembly (Helsinki, 1964) and all applicable amendments laid down by the World Medical Assemblies, in particular the Declaration of Helsinki as amended in 1996 for clinical trials with medicinal products in the EU, and the International Conference on Harmonisation (ICH) guidelines for good clinical practice (GCP), all applicable laws, rules and regulations.

This clinical trial will be recorded in a free, publicly accessible, internet-based registry, no later than 21 days after the first patient enrollment, in compliance with applicable regulatory requirements and with Sanofi public disclosure commitments.

### **12.2 INFORMED CONSENT**

The Investigator (according to applicable regulatory requirements), or a person designated by the Investigator, and under the Investigator's responsibility, should fully inform the patient of all pertinent aspects of the clinical trial including the written information giving approval/favorable opinion by the ethics committee (institutional review board/independent ethics committee [IRB/IEC]). All participants should be informed to the fullest extent possible about the study, in language and terms they are able to understand.

Prior to a patient's participation in the clinical trial, the written informed consent form should be signed, name filled in and personally dated by the patient (or by the patient's legally acceptable representative, if required by local laws, for those who are able to be consented but not able to sign the form), and by the person who conducted the informed consent discussion. A copy of the signed and dated written informed consent form will be provided to the patient.

If informed consent is obtained under special circumstances (emergency, from a guardian, minor, etc.), the method should be specified following the ICH requirements. The first part of the section should be adapted, keeping the point as appropriate.

Prior to the optional collection of blood for pharmacogenetics, the pharmacogenetic informed consent form must be obtained from the patient. This process includes a signing of the form with the name spelled out, and personally dated by the patient (or by the patient's legally acceptable representative, if required by local laws, for those who are able to be consented but not able to sign the form), and by the person who conducted the informed consent discussion. A copy of the signed and dated written optional informed consent form will be provided to the patient.

Similarly, prior to the optional collection of blood (plasma/serum) for Future Use Samples the informed consent form must be obtained from the patient in the same manner described above. Both informed consent forms for pharmacogenetics and Future Use Samples must be reviewed and approved by the Sponsor prior to submission to the appropriate ethics committee (IRB/IEC) for approval/favorable opinion.

### **12.3 HEALTH AUTHORITIES AND INSTITUTIONAL REVIEW BOARD/INDEPENDENT ETHICS COMMITTEE**

As required by local regulation, the Investigator or the Sponsor must submit this clinical trial protocol to the health authorities (competent regulatory authority) and the appropriate IRB/IEC, and is required to forward to the respective other party a copy of the written and dated approval/favorable opinion signed by the chairman with IRB/IEC composition.

The clinical trial (study number, clinical trial protocol title and version number), the documents reviewed (clinical trial protocol, informed consent form, Investigator's Brochure with any addenda or labeling documents (summary of product characteristics, package insert) Investigator's curriculum vitae [CV], etc.) and the date of the review should be clearly stated on the written (IRB/IEC) approval/favorable opinion.

The IMP will not be released at the study site and the Investigator will not start the study before the written and dated approval/favorable opinion is received by the Investigator and the Sponsor.

During the clinical trial, any amendment or modification to the clinical trial protocol should be submitted to the health authorities (competent regulatory authority), as required by local regulation, in addition to the IRB/IEC before implementation, unless the change is necessary to eliminate an immediate hazard to the patients, in which case the health authorities (competent regulatory authority) and the IRB/IEC should be informed as soon as possible. They should also be informed of any event likely to affect the safety of patients or the continued conduct of the clinical trial, in particular any change in safety. All updates to the Investigator's Brochure or labeling information, will be sent to the IRB/IEC and to health authorities (competent regulatory authority), as required by local regulation.

A progress report is sent to the IRB/IEC at least annually and a summary of the clinical trial's outcome at the end of the clinical trial.

